#### 4.10 Cognitive tests

**Multi-Source Interference Task :** The Multi-Source Interference Task (MSIT) is a cognitive paradigm that was designed to reliably identify the cingulo-frontal-parietal cognitive/attention network (CFP network) within individual subjects (Bush et al., 2006). Among other relevant brain regions, the pre-SMA and dorsal anterior cingulate cortex are activated in this 10-15 task when performed inside of the scanner. We will use this cognitive paradigm to identify our target of stimulation on an individual-subject basis.

Briefly, the MSIT presents a string of 3 numbers to subjects, which can be different combinations of 0,1,2,3 in which 2 numbers are the same and one is different (e.g. 100, 323, 221). Subjects are asked to identify what number is different by pressing one of 3 buttons available in the response box. Some trials will be congruent (e.g. 100) and some incongruent (010), depending on the position of the number that is different. The test also involves emotional stimuli to enhance the discriminative power of the task. The emotional stimuli are images that have been used in other studies involving patients with MDD at MGH and have been approved by the IRB (i.e. protocol number 2011P002821). Because emotional stimuli are involved in the task, the clinician will provide a verbal warning prior to the task and debrief with the patient immediately following.

Analyzing the brain response to these congruent and incongruent trials has been shown to robustly identify these brain networks and regions involved in executive functions at the individual level in healthy and patient populations (Bush et al., 2006).

**Pattern Recognition Task:** The pattern separation task is a high throughput behavioral task that captures the input-output transformation function characteristic of pattern separation processes (Stark et al., 2013). For example, if you park your car in the same lot everyday, but not the same space, pattern separation is thought to be involved in the process of you finding your car everyday despite being in a different space; this may be dysfunctional in people with depression. In this task, patients are shown a series of every-day objects (e.g., a car, garden tool, food, etc.) and are asked to identify the objects as being indoor or outdoor objects. Immediately after this, a second part of the task is started in which the patients are shown another series of objects. They are asked to call the objects as “old” if they have seen the objects before in the task, “new,” or “similar.” As previously done by Stark and colleagues, (2013) a third of the objects in the testing phase are “old”, “similar” and “new”. Identifying a “similar” object correctly conveys pattern separation, whereas, incorrectly identifying it as “old” conveys pattern completion. By plotting responses as a function of object similarity, we can generate an input-output transfer curve. This task will serve the purpose of rapid assessment of putative changes in pattern separation.

**Voice Pattern Recognition Task:** The content and quality of vocal production may be a valuable marker of health information. Vocal production, for example speech, contain rich information in both the content (linguistic) and quality (non-linguistic) characteristics of sound information.

Previous research has used vocal samples to predict important markers of cognitive and affective state. From the non-linguistic information of speech, including but not limited to the

information about the pitch, phonemes, and power spectrum of the vocal signal, researchers have been able to predict with high accuracy the cognitive load of an individual at a given moment. For example, vocal quality changes during increases in cognitive load (Le et al. 2011); cognitive load may reflect increasing difficulty of a mental task or suppressing automatic reading response to name the color of a text instead of the word of the text (MacLeod 1991). Similarly, researchers have used vocal quality to predict negative affect in the context of depression (Cummins et al. 2015). The features used to predict cognition and affect can be extracted from small samples of speech under various conditions, but to apply them for the prediction of health information, the collection of these data must be scalable and easy to use.

On a smartphone or tablet at the study site, participants will be administered a series of voice tasks via a mobile application ('app'). The devices used for the voice tasks are study team devices, i.e. are not the participant's personal devices. Additionally, no personal identifiers will be collected, shared, or stored through the mobile application. At study visits 1, 7, 13, 19 and 25 (screening, baseline, treatment/sham, and follow-up), participants will be given one or more voice task (see below) to be recorded on the smartphone or tablet. These tasks include:

i. A Stroop task. In the Stroop task, the participant is instructed to read out loud the color of the word presented on the screen. The research study application then presents words in succession. In a low cognitive load condition, the color of the word matches the text of the word (the word "blue" in blue-colored text), and the participant says the color. In a higher cognitive load condition, the color of the word does not match the text of the word (the word "purple" in yellow-colored text), and the participant must inhibit the automatic reading of the text in order to correctly name the color. Sometimes the text of the word is also emotionally salient ("happy" or "angry") or will vary in size, shape, color, font, duration on the screen, position on the screen, saturation, brightness, or contrast.

ii. A digit span task (DST). In the DST, participants are shown and read a sequence of numbers, ranging from 1 to 12 digits depending on difficulty condition. They are then sometimes read a brief sentence (eg. "the dog ran through the woods."). They are then asked to speak out loud the digits that were presented earlier and/or the sentence.

iii. A sentence/passage reading. In this portion, participants are shown text and asked to read it out loud. This ranges from holding a single syllable (eg. "ahhhh"), to a diadochokinetic task (repeating syllables like "PA, TA, KA"), to reading a simple sentence (e.g. "the horse trotted around the field at a brisk pace," or "Okay Google"), to reading a longer passage.

iv. Free response portion. In this portion, participants are given a specific prompt or may select a prompt from a list of options, for example, "how is the weather today?" or "describe your morning." The participants are instructed to freely respond to the prompt for a set period of time ranging from 30 seconds to 3 minutes.

Together, these tasks present a varied set of speech and sound data for each participant.

#### **4.11 Data Collection Forms**

All study clinicians and subjects will be blind to randomized treatment assignment.

A number of procedures are in place to assure data integrity and protocol adherence. We will use Research Electronic Data Capture to support direct data entry by patients and study staff. REDCap is a free, secure, HIPAA compliant web-based application hosted by the Partners HealthCare Research Computing, Enterprise Research Infrastructure & Services (ERIS) group. Web-based surveys rely on a study-specific data dictionary defined by members of the research team with planning assistance from Harvard Catalyst/The Harvard Clinical and Translational Science Center EDC Support Staff. These support staff will then oversee the automated export of study data from REDCap to a relational study database in Microsoft Access 2000, allowing for systematic data querying and checking.

Self-report measures will be completed by participants on a computer, directly into REDCap, thus minimizing errors due to data entry. For clinician-administered measures, all clinicians will enter responses directly in REDCap.

To minimize missing data for self-report forms, we will program missed question warnings in REDCap that will alert participants in real-time if they inadvertently skip a question. Participants may then go back and answer any missed questions, or, if they intentionally skipped questions, they may ignore the warning message and continue answer the remaining questions. We will also program real-time range checks in REDCap that generate error messages if a value outside the acceptable range is entered for a given field. To ensure confidentiality, data will be identified in the database only by subject number, visit number, and date of visit. By recording the study data in this manner, the information can be considered 'de-identified' and therefore compliant with the Standards for Privacy of Individually Identifiable Health Information ("Privacy Rule") of the Health Insurance Portability Act of 1996 (HIPAA). Any data that is transmitted electronically will be fully encrypted and password protected. Subjects' names will not be entered into the database; each will be uniquely identified only by an ID number. Consent forms, any hard copy PHI, and any study measures that are completed on paper will be kept and filed in locked office cabinets.

#### **4.12 Data Management**

The study biostatisticians ([name]) will oversee management of the study database. The principal investigators, [name] and [name], are ultimately responsible for the quality of the data collection and overall conduct of the study, and directly supervise the study coordinators and data management staff at MGH and NYUSOM, respectively. Data management will include clinician and patient rated assessments (see assessments), screening data, fidelity data, visit adherence data and rater reliability data and safety reporting. Weekly reports from REDCap will monitor subject enrollment, completion, attrition, and individual subject progress as well as the completion of critical assessments. Additional reports will be done as needed to monitor baseline characteristics, protocol adherence, and other issues of interest.

All measures that are completed on paper will be entered by the RA into REDCap, and a two pass verification system will be used to minimize any data entry errors. All records in

REDCap have a form completion status that may be Incomplete (appears as a red circle in Record Status Dashboard), Unverified (yellow circle), or Verified. The RA initially entering data will save each record entered as Unverified (at which point it will appear as a yellow circle in the Record Status Dashboard). A second RA at each site will then go into each unverified record, compare each entered value against the paper source document, make any corrections, and then re-save the record as Verified (at which point it will appear as a green circle in the Record Status Dashboard). The color coding system built into REDCap readily allows for identification of unverified records.

#### **4.13 Training**

Trained study clinicians blind to randomized treatment assignment will administer diagnostic assessments and rating scales. All raters will be experienced clinicians who will have undergone specific training to criteria in the use of the study measures. Any new raters will undergo training. Periodically, all study clinicians will co-rate an audiotape during a staff meeting. These duplicate ratings will be used both to calculate kappa coefficients and for supervision. Differences between raters will be discussed during supervision to identify reasons for disagreement and improve inter-rater reliability. These procedures will help us ensure that study clinicians refine their diagnostic skills and will also establish common guidelines for ongoing use in diagnostic decision-making. Inter-rater agreement will be assessed via evaluation of recordings of diagnostic interviews. Kappa coefficients will be calculated every 12 months. If reliability falls below criteria ( $ICC \geq 0.8$  for QIDS-C), study clinicians will be retrained.

#### **4.14 Randomization Procedure and Blinding of the Study**

The study statistician will provide the two study sites (MGH and NYUSOM) randomization codes (block randomization) which will be pre-loaded in the Litecure devices (TPBM-1000). The randomization codes will differ from the study ID assigned at the time of screening. The randomization codes will be two digit only to prevent any confusion. Study ID and randomization code will be matched at the time of the randomization in the subject binder and in a master list of study subjects at each site. In order to administer the treatment the study investigator will enter twice the randomization code in the Litecure instrument. In the event that a medical emergency will necessitate unblinding of a subject's treatment modality, the site's Principal Investigator (or Subinvestigator in the event that the PI is not readily accessible at the time of the medical emergency) will be able to retrieve the unblinding information from on-site sealed envelopes with codes paired to corresponding treatment.

Since this is a double-blind, sham-controlled study, measures have been taken to assure that the integrity of the blinding of the treatment modalities remains intact. The two means of assuring that the treatment modalities will not be disclosed to either subjects or site research personnel include automated LED control sensor based on the temperature of the skin. Also, the introduction of a rating scale for subjects and raters to assess their best guess on treatment assignment.

The performance/output of all visible and audible indicators is identical for all three treatment modalities, (i.e. other than the emission of invisible light radiation, the behavior of the system is identical for all).

#### ***4.15 Compensation***

Subjects will be compensated \$12.50 per treatment visit, for a total of \$300 if all twenty four treatment visits are completed. Compensation will be provided after Weeks 2 (\$50), 4 (\$50), 6 (\$50), and 8 (\$50), 10 (\$50) and 12 (\$50), and will be pro-rated for missed treatment visits.

#### ***4.16 Accountability/Investigational Product Control***

U.S. federal law and ICH Guideline E6 § 5.14 requires that all investigational medical devices be strictly controlled. All study devices must be kept in a secured area at the clinical sites in compliance with all applicable FDA (U.S. sites) regulations.

The Principal Investigators or designated study site personnel who verify the receipt of the devices/device accessories must complete the Device/Accessories Acknowledgment Form and fax a copy to Litecure Inc. Device Accountability and Acknowledgment Logs will be maintained at each study site. These logs will list all equipment received, the receiving date, the serial number of each device. Study site personnel will initial the log each time the device is used. TPBM-1000 use will also be recorded on the appropriate CRF.

Malfunctioning devices and device accessories, including all components, will be returned to Litecure Inc. for investigation, at Litecure expense.

#### ***4.17 Clinical Adverse Events***

##### **4.17.1 Overview and Definitions**

All adverse events will be recorded from the time of Informed Consent through study completion, or termination. The Adverse Event CRF must be completed and submitted to the IRB, FDA, and Litecure, as required. Regulations for adverse event handling and reporting contained in the FDA and ICH Guidelines will be adhered to.

Consideration of Adverse Events will hereafter consist of Adverse Events, Serious Adverse Events, and Adverse Device Effects, including Anticipated Adverse Device Effects and Unanticipated Adverse Device Effects.

- Adverse Event is defined as any untoward/undesirable clinical occurrence in a clinical investigation of a subject using a device and/or product and which does not necessarily have a causal relationship with this treatment. An Adverse Event can therefore be any unfavorable and/or unintended sign, symptom, or disease temporally associated with the use of a device product, whether or not considered

related to the device product. Only abnormal laboratory values that are deemed clinically significant by the investigator will be classified as adverse events.

- Serious Adverse Event is defined as any untoward/undesirable adverse experience that results in any of the following outcomes: 1) death; 2) a life-threatening adverse experience; 3) inpatient hospitalization or prolongation of existing hospitalization; 4) a permanent/persistent or significant disability/incapacity or a congenital anomaly/birth defect; 5) important medical events that may not result in death, be life-threatening, or require hospitalization may be considered a serious adverse experience when, based upon appropriate medical judgment, they may jeopardize the subject and may require medical or surgical intervention to prevent one of the outcomes listed in this definition.
- Anticipated Adverse Device Effect is defined as any adverse effect related to the device or procedure, which is identified in the protocol.
- Unanticipated Adverse Device Effects is defined as any serious adverse effect on health or safety or any life-threatening problem or death caused by, or associated with, a device, if that effect, problem, or death was not previously identified in nature, severity, or degree of incidence in the investigational plan or application (including a supplementary plan or application), or any other unanticipated serious problem associated with a device that relates to the rights, safety, or welfare of subjects.

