**Endpoints:**

**Safety** - The safety endpoints will evaluate the TLT and sham groups for differences in tolerability through 12 weeks of follow-up.

**Efficacy** - The efficacy endpoint will be the antidepressant effect of TLT through week 12, as assessed using the QIDS-C scale.

**Engagement of Neuro-Inflammation** – The effect of TLT on inflammation will be assessed at week 6 and 12 by measuring the plasma levels of IL6, TNF- $\alpha$ , IL-1 $\beta$  as primary cytokines (compared to baseline).

**Engagement of Cognitive circuitry** – The effect of TLT on cognition will be assessed at week 6 and 12 by measuring pattern recognition and cognition with emotional stimuli (compared to baseline).

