#### 4.8.4 Termination

We will encourage subjects to continue enrollment in the study via follow-up visits regardless of discontinuation of the TLT/ sham. At the end of the study, we will refer the subjects to their counselor and /or psychiatrist. If the CGI-S increases more than 2 points during the study, the subject will be counseled to start or change to an FDA-approved antidepressant medication. If the CGI-S increases above score-5 or if a subject becomes actively suicidal based on the C-SSRS scale, the subject will be counseled to start (or switch if already on) an FDA-approved antidepressant medication. Subjects who are deemed actively suicidal and are in imminent danger will be escorted to the local psychiatric Emergency Department at MGH or NYUSOM for evaluation and subsequent hospitalization; they will also be terminated from the study. If the subject is appropriate for outpatient monitoring, the subject will be followed with frequent appointments outside the study. Each subject will have the Investigator's contact information as well as instructions on how to call for emergency services, if needed.

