#### **4.17.2 Safety Monitoring**

The study subjects will undergo frequent clinical evaluations including depressive scores, concomitant medications, adverse events, and serious adverse events and unexpected device events will be recorded from study entry through completion. Additionally, doctors must monitor a subject's safety by asking the subjects frequently about the subject's own comfort during treatment application.

If skin erythema is present, treatment will be suspended. Patients will be instructed to contact the study site principal investigator or a member of his staff at any time between visits concerning adverse events or worsening of symptoms. If at any study visit the subjects' clinical condition is significantly worsened from baseline (operationalized as the clinical global impression severity score, CGI-S, of 6 or higher) or if a subject becomes actively suicidal with intent and/or plan, based on the C-SSRS scale and/or the clinical interview, the subject will be offered to start an antidepressant medication. If the subject were deemed at imminent danger as a result of suicidality, s/he would be discontinued from the study and referred to appropriate clinical treatment (see 4.8.4 Termination).

The two site Principal Investigators (Drs. [name] and [name]) will have bi-weekly conference calls (which will include study RAs); during these conference calls they will discuss all Adverse Event reports to identify any safety concern, based on such concerns they will be able to decide temporary discontinuation of study enrollment, modifications of the study protocol, or to terminate the study.

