Additionally, A Data and Safety Monitoring Board (DSMB), consisting of at least 2 clinicians and one biostatistician not directly involved in the study, will review SAEs annually. Research assistants responsible for data collection and storage will be aware of and comply with all regulatory requirements related to adverse events. In the event that a patient becomes ill or is injured as a direct result of study participation, medical care will be made available. All adverse events (and device events) will be followed to resolution and reported to the MGH IRB as serious in the event that **1.** they are unanticipated and possibly related to the study (same reporting as SAE) or **2.** if they meet any one of the following criteria: Any fatal event, immediately life-threatening event, permanently or substantially disabling event, event requiring or prolonging inpatient hospitalization, or any congenital anomaly. This also includes any event that a study investigator judges to impose a significant hazard, contraindication, side effect, or precaution.

Expedited review will occur for all events meeting the FDA definition of Serious Adverse Events (SAEs) – i.e., any fatal event, immediately life-threatening event, permanently or substantially disabling event, event requiring or prolonging inpatient hospitalization, or any congenital anomaly. This also includes any event that a study investigator or the DSMB judges to impose a significant hazard, contraindication, side effect, or precaution. For purposes of this study, all SAEs will be required to be reported to the DSMB, regardless of any judgment of their relatedness to the study device. All relevant information will be reported to the DSMB for each SAE including information about the event and its outcome, dosing history of all study TLT applications, concomitant medications, the subject's medical history and current conditions, and all relevant laboratory data. Per Partners IRB protocol, the principal investigator at each site will report all serious unanticipated adverse events to Insight/eIRB within 5 working days/7 calendar days of the date the investigator first becomes aware of the problem. If at any time during the course of the study, the DSMB judges that the risk to subjects outweighs the potential benefits, the DSMB shall have the discretion and responsibility to recommend that the study be terminated.

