#### **4.17.5 Deaths**

Deaths which must be reported to Litecure Inc include all deaths while participating in the study.

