Risk of Worsening of Depression, Suicidality & Manic Switch: Worsening of depression and increased suicidality are possible complications of antidepressant treatments prescribed to subjects with MDD. We will minimize this risk by selecting only subjects who do not present active suicidal ideation at screening. We will also discontinue any subject who develops active suicidal ideation during the course of the study (C-SSRS) and is deemed at imminent danger; we will then arrange for appropriate levels of care and standard antidepressant treatment (see 4.8.4 Termination). Manic switches are possible adverse events and will be closely monitored during antidepressant treatment as well. Our tight schedule of clinical study visits will allow early recognition of treatment-emergent suicidal ideation or prodromal hypomanic signs. Subjects who develop mania or hypomania will be discontinued and provided appropriate level of care.

Answering detailed questionnaires may create a mild degree of inconvenience for the subjects.

Length of testing for cognitive circuitry:

The total length of this task takes a total of 40 minutes at baseline and 40 minutes at week 3, 6, 9 and 12. There is no expected risk to the patients beyond the 40 minutes of sitting in front of computer for testing and possible experience of startle. Every effort will be made to ensure that the patients are comfortable and safe during this period, and the study can be stopped at any time. Beyond these issues, there is minimal or no risk to the patients.

Risk of Bruising

Venipuncture might result in accidental bruising at the sight of blood drawing on the forearms.

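### No rule captures new serious events or deaths after a subject is terminated, although the protocol terminates those in imminent suicidal danger

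*Protocol*

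**What the plan says.** The recording window is in Protocol 4.17.1: "All adverse events will be recorded from the time of Informed Consent through study completion, or termination". Section 4.17.2 words it differently, without the reference to termination: adverse events, serious adverse events and "unexpected device events will be recorded from study entry through completion". The adverse-event tables in 5.7 also run to study completion.

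Three sections deal with subjects in imminent danger from suicidality:

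- 4.8.4 sends them to the emergency department for evaluation and hospitalization and adds that "they will also be terminated from the study".
- 4.17.2 says that "s/he would be discontinued from the study and referred to appropriate clinical treatment".
- 4.20.1 says "We will also discontinue any subject who develops active suicidal ideation during the course of the study (C-SSRS) and is deemed at imminent danger". It also discontinues subjects who develop mania or hypomania, without saying whether from treatment or from the study.

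The horizon of the safety comparison is in the Study Summary: "The safety endpoints will evaluate the TLT and sham groups for differences in tolerability through 12 weeks of follow-up".

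Several provisions bear on what happens after exit. In 4.17.2, "All adverse events (and device events) will be followed to resolution"; fatal events are among those reported as serious to the IRB, and every SAE goes to the DSMB whatever its relatedness. In 4.17.5, "Deaths which must be reported to Litecure Inc include all deaths while participating in the study". Section 4.8.4 encourages subjects who stop TLT or sham to keep attending, and 4.19.1 asks for an exit visit, where feasible, that includes the C-SSRS and the adverse-event form. The SAP does not address safety.

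**The concern.** Worsening, suicidality and manic switch are risks that 4.20.1 itself names. Under the rules as written, the appearance of such a harm is also what ends the subject's observation. If one arm produces more of these exits, that arm also loses more of the later time in which an attempt, a further hospitalization or a death could be counted. Censoring of that kind is informative, and it biases the comparison toward no difference or toward the more harmful arm.

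Safety and tolerability are a stated aim, with the hypothesis in 5.2 that TLT is safe and well tolerated. In a trial of 50, that conclusion can turn on one or two serious events.

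**Working it through.** The plan states no figure on this point, so there is none to reproduce. The check has two parts: what the text covers, and how many subjects the gap could touch.

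**1. Coverage after termination, by type of event**

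| Event | Provision | Covered after termination? |
|---|---|---|
| Present at the exit assessment | 4.19.1 exit visit | Yes, if the visit is feasible |
| Already open at exit, such as the crisis that led to removal and any hospitalization | 4.17.2, followed to resolution | Yes under 4.17.2; 4.17.1 stops recording, so the two conflict |
| New SAE or suicidal behavior after exit | 4.17.2 and 4.17.4 reporting routes | Not stated: they say where a known event goes, not how long events are sought |
| Death after exit | 4.17.2 lists fatal events; 4.17.5 covers reports to the device company | Not stated: neither sets a window, and there is no vital-status check |

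The encouragement in 4.8.4 applies to stopping TLT or sham, not to being terminated from the study. The same section places outpatient monitoring after such a crisis outside the study. The gap is therefore new events and deaths after termination and before the end of the 12-week horizon.

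**2. Size**

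The documents give no rate of removal for imminent suicidal danger, so I assume p = 1%, 2% or 5% with N = 50 (Protocol 5.1). The expected number is N × p, and the chance of at least one is 1 − (1 − p)^50.

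- p = 1%: 50 × 0.01 = 0.5 subjects; 1 − 0.99^50 = 39%.
- p = 2%: 50 × 0.02 = 1.0 subject; 1 − 0.98^50 = 64%.
- p = 5%: 50 × 0.05 = 2.5 subjects; 1 − 0.95^50 = 92%.

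Planned safety observation is 50 × 12 = 600 subject-weeks. A terminated subject loses at most 12 of these, so the loss is at most 0.5 × 12 / 600 = 1% to 2.5 × 12 / 600 = 5%. If exits are spread evenly over the 12 weeks (assumption), the mean loss is 6 weeks each, which halves this to 0.5% to 2.5%. The lost time is small; what matters is which subjects lose it.

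**3. Why one missed event counts**

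With no events in 50 subjects, the exact one-sided 95% upper bound on the event rate is 1 − 0.05^(1/50) = 5.8%. With one event, the bound solves (1 − p)^50 + 50p(1 − p)^49 = 0.05, which gives p = 9.1%. A single serious event missed after termination thus moves the bound from 9.1% to 5.8%.

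**The case against.** The strongest reply is that the case of most concern is the one most likely to be covered. A subject removed for imminent suicidal danger is sent for hospitalization, inpatient hospitalization is an SAE by the definition in 4.17.1, and that SAE is open at exit. Section 4.17.2 follows it to resolution, and 4.17.3 requires an outcome and, where applicable, a resolution date. A later attempt or death within the same crisis could be recorded as the outcome of that event. This stands, and it narrows the gap. It does not close it: 4.17.1 stops recording at termination, and an event that begins after the crisis has resolved falls under no rule.

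It can also be said that termination in 4.17.1 is not defined, and that 4.17.2 and 5.7 speak only of completion. Subject-level termination is the natural reading of 4.17.1, but three different statements of the window are themselves a reason to settle on one.

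Three stronger readings are tempting and not supported:

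- **That deaths after exit are excluded by 4.17.5.** That section governs reports to the device company only, and its list is inclusive rather than exhaustive. Section 4.17.2 deals with fatal events separately.
- **That the 12-week safety endpoint is not observed.** Subjects who stay have the adverse-event form and SAFTEE-SI through Visit 25, and those who leave have an exit visit if feasible. Observation is incomplete for leavers only.
- **That the planned 24% loss before week 6 (0.24 × 50 = 12 subjects) measures the problem.** That is loss from all causes. The documents give no reasons for it and do not link it to harm. It includes kinds of loss, such as withdrawn consent and failed contact, that a longer recording window could not recover.

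**Conclusion.** The concern holds in a limited form. Recording stops at termination under 4.17.1, subjects in imminent suicidal danger are removed from the study, and nothing provides for capturing new serious events, suicidal behavior or deaths after that. For those subjects the 12-week comparison is incompletely, and potentially informatively, observed. The same applies to mania or hypomania if discontinuation in 4.20.1 means leaving the study, which it does not say.

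The number affected is not documented and is probably small: about 0.5 to 2.5 of 50, with a 39% to 92% chance of at least one, under assumed rates of 1% to 5% for imminent suicidal danger. No bias in a particular direction has been shown; it would arise only if such exits differ by arm. This is a worthwhile, low-cost improvement to data capture, and it takes no view on when a subject should be terminated.

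**What to change.** In 4.17.1, replace the end of the recording window with one safety-observation period, for example: *adverse events are recorded from informed consent to each subject's scheduled final visit date (week 13), whether or not the subject has been terminated, unless consent to contact is withdrawn; for terminated subjects at least serious adverse events, suicidal behavior and vital status are obtained by telephone or from the treating clinician.*

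Then align the other sections to that period:

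- 4.17.2: use the same end date, and state that following open events to resolution continues past it where needed.
- 4.17.5: state the same period for reports of deaths to the device company.
- 5.7: tabulate these events by phase of the sequential parallel design and the treatment assigned in that phase, flagged as post-termination. State that a sham subject terminated before the week-6 randomization stays under the phase-1 assignment.

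The cost is protocol and consent wording and a few extra contacts, with no new procedure or staff. Some contacts will fail, and the safety table may look less favourable. The clinical termination rules in 4.8.4, 4.17.2 and 4.20.1 are left as they are.
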